6.4.2 Intent-to-Treat Population

The intent-to-treat (ITT) population includes all subjects who are randomized. The ITT Population will be used for all efficacy analyses and all baseline demographics. Subjects will be grouped according to the treatment to which they are randomized in all efficacy analyses. This population will be used for the primary efficacy analysis, demographics, and baseline characteristics.

6.4.3 Per-Protocol Population

The primary efficacy analyses will be repeated using the per-protocol (PP) population in order to confirm the results based on the ITT population. The PP population includes all subjects in the ITT Population who fulfill the following criteria:

- Subject randomized to the SMT + Albutein 20% arm will be excluded from the PP population if:
 1. the subject does not receive at least 80% of the expected doses prior to the date of events (death or transplantation) or study discontinuation / completion date,
 2. the subject misses 4 or more consecutive weeks
- Subject has no major protocol violations which might have an impact on primary efficacy analysis.

6.5 Hypothesis Testing and Multiplicity Adjustments

All statistical tests will be 2-sided with significance level fixed at 0.05.

The fixed-sequence testing method will be used to adjust for multiplicity in the analyses of the secondary efficacy endpoints (using the ITT population). Specifically, the superiority of SMT + Albutein 20% versus SMT alone for the secondary efficacy endpoints will only be tested if the superiority for the primary efficacy endpoint is demonstrated at the 2-sided significance level of 5% (for ITT population).

For the secondary efficacy endpoints, each subsequent hypothesis is tested only if the superiority for the previous comparison(s) listed below has been demonstrated at a 2-sided significance level of 5%. The order in which the null hypotheses will be tested is predetermined for the secondary efficacy endpoints as follows:

1. Time to death through 1 year after randomization
2. Time to liver transplantation or death through 6 months after randomization
3. Time to death through 6 months after randomization
4. Time to liver transplantation or death through 3 months after randomization
5. Time to death through 3 months after randomization
6. Total number of paracenteses
7. Incidence of refractory ascites according to the ICA criteria

No other adjustments for multiplicity are planned. P-values will be displayed for all the above pre-specified tests for completeness; interpretation and reporting of significant hypothesis test results will follow the fixed sequence approach described.

GRIFOLS	Bioscience Industrial Group	Number	IG1601	Version	2.0	Status	Effective	Effective Date	09-Sep-2024	Page	24 of 52
		IG1601	Statistical Analysis Plan								

7 Subject Disposition and Demographics

Unless otherwise noted, all demographics listings and summaries will be based on the ITT population. Subjects who were incorrectly stratified at the time of randomization will be listed and summarized.

7.1 Subject Disposition

Subject disposition will include the number of all subjects screened, screen failures, number and percentage of subjects in each analysis population including the ITT population, Safety population, and PP population.

The number and percentage of subjects in the ITT population who discontinue from the study will be summarized by reason for discontinuation.

Disposition status will be listed for all subjects, including those who were screened but not randomized.

7.2 Protocol Deviations

Deviations from the protocol will be identified during the study and evaluated before the database lock. Protocol deviations will be listed and will include category, severity (i.e., minor, major, or critical), and description of deviation. Summaries of incidences of deviations and subjects experiencing deviations will be presented for the following: any deviation, critical deviations, major deviations. Deviations related to COVID-19 will also be summarized as described above.

7.3 Demographics

Demographics (age, sex, race, ethnicity, country and region in Europe), baseline weight, and stratification factors for randomization will be listed and summarized. Subjects who were incorrectly stratified at the time of randomization will be listed and summarized.

Baseline characteristics listed above will be compared to evaluate possible imbalance by using Student's t test will be used for continuous variables, Chi-square test for binomial or nominal variables, and Poisson model for count variables (with adjustment for overdispersion). All demographic and baseline characteristics data will be listed. Summaries will be provided by treatment group for ITT.

In addition, the following baseline characteristics will be summarized; ACLF Grade, Ascites Grade, Ascites Refractory Occurrences, Ascites Refractory Type, CLIF-C ACLF Score, CLIF-C AD Score, CLIF-C OF Total Score, Child-Pugh Score, MELD Score.

GRIFOLS	IG1601 Statistical Analysis Plan			
	Number	BIG-CL-SP-000319	Version	2.0
	Status	Effective	Effective Date	09-Sep-2024
	Page			25 of 52

7.4 Medical History

Medical history terms are coded using the Medical Dictionary for Regulatory Activities (MedDRA) (version within one year of data base lock), associating lower-level terms with preferred terms (PTs) and system organ classes (SOCs). All medical history information will also be listed. A medical history summary will present the number/percentage of subjects with at least one history event by treatment, SOC and preferred term. Summaries will be provided by treatment group.

7.5 Disease History

Disease history including recent endoscopic procedures, recent abdominal ultrasound, and identification of cirrhosis etiology and the corresponding confirmation method of the cirrhosis will be listed and summarized by treatment group. Each subject may have more than one response selected for cirrhosis etiology; all recorded combinations will be included in the corresponding summary.

8 Treatments (Albutein) and Other Medications

Unless otherwise noted, all listings and summaries of treatments and medications will be based on the Safety population.

8.1 Prior and Concomitant Medications

Summaries of all medications taken during the course of the study will be presented in tabular form and coded using Anatomical Therapeutic Chemical (ATC) classification codes via the World Health Organization Drug classification Dictionary (WHO-DD), a version within one year of the data base lock will be employed. All medications will be summarized by treatment and sorted alphabetically by medication class (i.e., ATC level 2) and medication sub-class (i.e., ATC level 4). If the ATC level 2 or 4 term is missing, the higher ATC level term will be used in the medication summary table and data listing.

All medications will be listed by subject, with prior/concomitant designation as defined in [Section 6.1.7](#). Prior and concomitant medications will be summarized in separate tables by treatment (including an overall summary for prior medications), medication class and medication subclass. At each level of summarization, a subject will be counted once per medication class or subclass.

8.2 Blood Products

All blood products used will be listed by subject and summarized in separate tables by treatment. The summary includes, but not limited to the following parameters: category

GRIFOLS	Number	IG1601	Statistical Analysis Plan
	Version	2.0	Page
	Effective	09-Sep-2024	26 of 52
	Status		
	Effective Date		

(SMT and other blood products), blood product type, amount, time since the start of use. At each level of summarization, a subject will be counted once per category and blood product type.

8.3 Extent of Exposure to Albutein 20%

For subjects randomized to SMT + Albutein 20%, all Albutein exposure details will be listed by visit.

An overall summary of exposure will present the duration of exposure (weeks), number of infusions received, number of subjects who had 4 or more missing consecutive infusions, and the total volume infused (mL). Duration of exposure is defined as [(date of last infusion – date of first infusion) + 10]/7. Interruptions, dose changes, and compliance are not considered in the calculation of duration of exposure.

Albutein infusion interruptions will be summarized by visit. Number of infusions, number and percentage of infusions with interruptions, and number and percentage of infusions with interruptions due to TEAE will be summarized.

8.4 Treatment Compliance for Albutein 20% Administration

Treatment compliance, infusion compliance, and overall compliance will be listed and summarized for the SMT + Albutein 20% group specific to the Albutein study drug treatment. In addition, the number and percentage of subjects with Albutein compliance <80%, 80% to \leq 120%, and >120% will be presented. Infusion compliance will be calculated as (number of actual infusions / number of infusions expected or planned) *100. For subjects that complete the study, the number of infusions expected is 37. For subjects who drop out from the study early, the number of infusions expected or planned will be calculated as [(date of end of study visit – date of randomization) / 10 + 1].

Treatment compliance will be calculated as (total volume infused / total volume prepared)*100. Missing visits will be excluded in the calculation.

Overall compliance will be calculated as (treatment compliance * infusion compliance)/100.

Treatment compliance for the SMT alone group is not applicable for any Albutein study drug compliance assessments.

Effective Date	09-Sep-2024
Page	27 of 52

Number	IG1601 Statistical Analysis Plan

GRIFOLS	Bioscience Industrial Group

9 Efficacy Analysis

All efficacy listings and summaries will be based on the ITT population. In addition, the primary and secondary efficacy summaries and analyses will be repeated for the PP population.

For the purposes of defining the analysis period for each of the efficacy analysis timepoints the following will be applied:

Analysis Timepoint	Analysis Period	Cut-Off Date
1 Year	362 Days	Randomization Date + 361 Days
6 Months	182 Days	Randomization Date + 181 Days
3 Months	92 Days	Randomization Date + 91 Days

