5.3.2 Discontinuation of Subjects from Treatment

If a subject receives a liver transplant, study treatment and all treatment-related assessments will be discontinued upon transplant. The criteria to determine when a subject becomes a candidate for liver transplantation is described in Section 5.3.2.1. The subject will continue to have subsequent planned visit assessment procedures performed.

Discontinuation of the treatment in subjects who receive a TIPS insertion will be at the discretion of the investigators. In case it is decided to discontinue the subject's treatment early, study treatment will be stopped and the subject will continue to have subsequent planned visit assessment procedures performed.

Adverse events that will determine temporary subject's discontinuation from study treatment include the following:

• Subjects developing severe bleeding, Albutein 20% infusions will be temporarily stopped until the bleeding episode is resolved. For subjects with variceal bleeding, Albutein 20% infusions will be temporarily stopped until the subject has received at least 2 banding sessions. Albutein 20% infusions will be resumed after the bleeding episode is resolved or after the subject has received at least 2 banding sessions, respectively.

Adverse events that will determine permanent subject's discontinuation from study treatment include the following:

- Anaphylactic shock or transfusion-related acute lung injury
- Severe AEs (ie, acute myocardial infarction, cerebral hemorrhage, cardiac failure, pulmonary edema, or intestinal necrosis) that precludes the continuation of the subject in the clinical study

Subjects with any one of these severe AEs will be discontinued from study treatment and all treatment-related assessments, and should continue to have subsequent planned visit assessment procedures performed.

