5.1 Overall Study Design and Plan

This is a phase 3, multicenter, randomized, controlled, parallel-group, and open-label clinical study to evaluate the efficacy of SMT + Albutein 20% administration versus SMT alone in subjects with decompensated cirrhosis and ascites.

Approximately 410 subjects with decompensated cirrhosis and ascites will be included in this study after obtaining written informed consent. The study population will consist of subjects who have been hospitalized for acute decompensation of liver cirrhosis with ascites (or with prior history of ascites requiring diuretic therapy) with or without ACLF at hospital admission or during hospitalization, but without ACLF at Screening.

There will be a screening period for enrollment of each hospitalized subject in the study. Screening should occur while the subject is hospitalized. Randomization must occur within 3 days (72 hours) of Screening, and it can occur while the subject is hospitalized or after discharge from the hospital. The first dose of Albutein 20% is to be administered on the same day as randomization (for the SMT + Albutein 20% group).

Randomization of subjects will be stratified by region (Europe or North America) and by whether or not subjects have been previously hospitalized for acute decompensation of liver cirrhosis prior to the most recent hospitalization for acute decompensation of liver cirrhosis with ascites as required by Inclusion Criterion #3v4. Within each stratum (i.e., each unique combination of region and history of hospitalization for acute decompensation of liver cirrhosis), eligible subjects will be randomized in a 1:1 ratio into 1 of 2 treatment groups:

- SMT + Albutein 20%
- SMT (control group)

SMT + Albutein 20% Treatment Group

Approximately 205 subjects will be randomized to the SMT + Albutein 20% treatment group. Screening should occur while the subject is hospitalized. Randomization must occur within 3 days (72 hours) of screening, and it can occur while the subject is hospitalized or after discharge from the hospital.

The first infusion of Albutein 20% is administered on the same day as randomization (Day 1) at the dose of 1.5 g/kg body weight (maximum 100 grams per infusion). Thereafter, subjects will receive Albutein 20% infusions at the dose of 1.5 g/kg body weight (maximum 100 grams per infusion) every 10 ± 2 days for the rest of the study (up to a maximum of 12 months). Subjects in this treatment group will also receive SMT.

SMT Group

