5.2.5 Month 12 / Early Discontinuation

All subjects will have assessments at Month 12 (Day 361 ± 2 days)/Early Discontinuation. Subjects in the SMT + Albutein 20% treatment group will receive an Albutein infusion at Month 12. All assessments and activities will be performed prior to treatment for SMT + Albutein 20% treatment group. In the SMT + Albutein 20% treatment group, vital signs and serum albumin concentration will also be recorded after Albutein infusion.

Subjects who discontinue from the study early will complete the assessments that are planned for the Month 12 visit.

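### SAP 8.4 expects 37 infusions from a transplanted subject who is followed to Month 12, so its compliance table understates adherence and disagrees with the dose count in SAP 6.4.3

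*SAP*

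**What the plan says.** SAP 8.4 defines the measure: "Infusion compliance will be calculated as (number of actual infusions / number of infusions expected or planned) *100". The denominator has two branches. The first is for completers: "For subjects that complete the study, the number of infusions expected is 37". The second begins "For subjects who drop out from the study early, the number of infusions expected or planned will be calculated as" and takes the days from randomization to the end of study visit, divides by 10 and adds 1. Neither branch covers a subject who stops infusions but stays in the study. The section also reports "the number and percentage of subjects with Albutein compliance <80"%, together with two higher bands.

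Protocol 5.3.2 says that after a liver transplant "study treatment and all treatment-related assessments will be discontinued upon transplant". It then keeps the subject in the later planned visits, so a transplanted subject can reach Month 12.

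SAP 6.4.3 uses a different window for the per-protocol population. An Albutein subject must receive "at least 80% of the expected doses prior to the date of events (death or transplantation"), or before study discontinuation or completion.

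**The concern.** The protocol requires infusions to stop at transplant, but the SAP 8.4 denominator keeps running to Month 12. Infusions that could not have been given are counted as missed. The same subject can be fully adherent under SAP 6.4.3 and far below 80% under SAP 8.4.

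The case is foreseeable, because transplant is a component of the primary endpoint. At stake is whether the compliance table can be read as a measure of adherence. As defined, it mixes protocol-mandated stops with missed dosing and does not separate them.

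**Working it through.** **Inputs**
- Interval: "every 10 ± 2 days for the rest of the study (up to a maximum of 12 months") (SAP 5.1).
- Last infusion: "Subjects in the SMT + Albutein 20% treatment group will receive an Albutein infusion at Month 12" (SAP 5.2.5), that is, Day 361.
- Infusion days: Protocol 7.2.1.2 and SAP 5.2.2 to 5.2.5.
- Infusions stop at transplant (Protocol 5.3.2), so none is credited on the transplant day.

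**1. The plan's own figure.** Day 1 (1) + Day 11 (1) + Months 1 to 11 (11) + treatment-only days (23) + Month 12 (1) = 37. The same count comes from (361 − 1)/10 + 1 = 37. The figure of 37 reproduces exactly for a full course.

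**2. The other branch.** If a transplanted subject is treated as a drop-out but has the end of study visit on Day 361, the formula again gives (361 − 1)/10 + 1 = 37. The choice of branch makes no difference.

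**3. A fully adherent subject transplanted on study Day T.** Infusions fall on Days 1, 11, 21 and so on. The number before Day T is floor((T − 2)/10) + 1.

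| Transplant day | Infusions received | SAP 8.4 (out of 37) | Received / due before transplant (SAP 6.4.3 window) |
|---|---|---|---|
| 91 | 9 | 24.3% | 9/9 = 100% |
| 181 | 18 | 48.6% | 18/18 = 100% |
| 271 | 27 | 73.0% | 27/27 = 100% |
| 291 | 29 | 78.4% | 29/29 = 100% |
| 292 | 30 | 81.1% | 30/30 = 100% |

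**4. Where the 80% line falls.** 0.80 × 37 = 29.6, so 29 or fewer infusions is below 80%. The 30th infusion falls on Day 1 + 29 × 10 = Day 291, so any transplant up to and including Day 291 is below the line. From Day 292 the figure is above 80% but still understated. Days 2 to 291 are 290 of 360 possible transplant days (81%). This is a share of days, not of transplants.

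**5. Visit window.** With every interval at 8 days, the 30th infusion falls on Day 1 + 29 × 8 = Day 233. With every interval at 12 days, it falls on Day 1 + 29 × 12 = Day 349. These are the limits for the last affected transplant day.

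**The case against.** **SAP 8.4 is descriptive and 6.4.3 stands alone.** This is the strongest point, and it holds. Section 6.4.3 sets its own counting window, which ends at transplant, and neither section refers to the other. Expected doses before transplant can be counted directly from the visit schedule. A reader might infer that transplanted Albutein subjects, all of whom have a primary event, would drop out of the PP population in one arm only. The documents do not support that: followed literally, the 8.4 figure removes nobody. The risk exists only if 8.4 is borrowed. That is conceivable, since it holds the only formula for expected infusions, reports a cut at the same 80%, and the PP definition in Protocol 9.7 refers to scheduled treatments without ending the count at transplant.

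**Transplanted subjects may not be completers.** SAP 8.4 does not define completing the study, and SAP 5.2.6 ties completion to 12 months of treatment. On that reading they leave the first branch, but step 2 shows that the second gives the same 37 at Day 361. The gap remains.

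**The bands are ambiguous.** SAP 8.4 defines treatment, infusion and overall compliance and does not say which one is banded. Treatment compliance (volume infused over volume prepared, missing visits excluded) would not show the effect. Infusion compliance does, and so does overall compliance, which multiplies the two. This limits the statement about the below-80% band but not the infusion compliance values themselves.

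**The label.** A reader might take the band to mean that these subjects are declared non-compliant. The SAP does not use that term; it reports a percentage band.

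**Conclusion.** The point holds as a minor error of definition. The number 37 is correct for a full course and wrong for a subject whose infusions the protocol ended at transplant. Such a subject, fully adherent until then, is reported at about 24%, 49% or 73% for transplant on Day 91, 181 or 271. The figure is below 80% for any transplant up to Day 291 (range Day 233 to Day 349), against 100% under the 6.4.3 window.

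This assumes follow-up to Day 361, every scheduled infusion given before transplant, none on the transplant day and, for the bands, that infusion or overall compliance is the measure used. The documents give no expected number of transplants, so the effect on the table as a whole cannot be sized.

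The ITT primary analysis is untouched, and the PP population as defined in SAP 6.4.3 is not altered.

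Subjects who stop infusions after TIPS or because of an adverse event, and who stay in follow-up, also receive a denominator of 37. SAP 6.4.3 does not end its count at those stops either, so the conflict between the two sections is specific to transplant.

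**What to change.** - In SAP 8.4, count expected infusions from randomization to the earliest of death, transplant, or study discontinuation or completion. Including death matches SAP 6.4.3.
- Exclude the transplant day and state a rounding rule. Putting the transplant date into the existing drop-out formula is not enough: for a transplant on Day 31 it expects (31 − 1)/10 + 1 = 4 infusions when 3 were due, which gives 3/4 = 75% for a fully adherent subject.
- State in SAP 6.4.3 that its expected doses are this same count.
- Name the compliance measure to which the bands apply.
- Tabulate separately the subjects whose infusions were permanently stopped for other reasons the protocol allows while they remained in follow-up.

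The cost is a few lines of SAP wording and one derived date. No data collection, dosing or clinical rule changes.

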5.3.5 Follow-up of Subjects Withdrawn from Study

If possible, blood samples will be obtained to complete all pertinent tests at the time of subject withdrawal. In all cases, the reason for withdrawal must be recorded in the eCRF and in the subject's records. No subject can be re-enrolled into the study after having been withdrawn from the study.

Subjects who receive any amount of IP and discontinue early from the study should have all Month 12/Early Discontinuation visit procedures performed at the time of withdrawal (preferably within 1 week of withdrawal).

All efforts should be made to collect the vital status of the subject (including data on liver transplantation, subject survival, and cause of death) at Months 3, 6, and 12.

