7.2.1.3 End of Study Visit for Subjects who Complete Study Treatment

Subjects will return to the study center within 1 week of study completion. End of study assessments in subjects who complete study treatment (up to 12 months) will include:

- Record concomitant medications
- Record AEs

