9.7 Subject Population for Analysis

There will be 3 analysis populations in this study; 2 populations for efficacy assessment and 1 population for safety evaluation.

The ITT population is defined as all subjects who are randomized. The ITT population will be used for all efficacy analyses. Subjects will be grouped according to the treatment to which they are randomized in all efficacy analyses.

The PP population is defined as the subset of subjects included in the ITT population who do not present major protocol violations which might have an impact on the primary efficacy analysis, complete at least 80% of the scheduled treatments and are not excluded from the study for interrupting the Albutein 20% treatment for more than 4 consecutive weeks (SMT + Albutein 20% treatment group subjects). The primary efficacy analyses will be carried out using the PP population in order to confirm the results based on the ITT population.

The Safety population is defined as the subset of patients who receive at least one SMT plus Albutein 20% treatment or SMT. Safety analyses will be based on this population. Subjects will be grouped according to the treatment they actually received in all safety analyses.

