5.2.6 End of Study for Completed Subjects

Subjects who complete the full 12 months of treatment will return within one week of study completion for collection of prior/concomitant medications and adverse events (AE).

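### SAP 8.4 counts fractions of infusions not yet due, so fully dosed early exits get infusion compliance below 80%; SAP 6.4.3 applies an 80% rule without giving any count

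*SAP*

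**What the plan says.** **Compliance table (SAP 8.4).** Three measures are defined for the Albutein arm:
- infusion compliance: infusions given over infusions expected;
- treatment compliance: volume infused over volume prepared, missing visits excluded;
- overall compliance: the product of the two, divided by 100.

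Subjects are then split at 80% and 120%, without a statement of which measure is split. Completers have 37 expected infusions. "For subjects who drop out from the study early, the number of infusions expected or planned will be calculated as" (end-of-study visit date − randomization date)/10 + 1, with no rounding rule.

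**Who has that visit.** Protocol 7.2.1.3 is titled "End of Study Visit for Subjects who Complete Study Treatment", and SAP 5.2.6 says "Subjects who complete the full 12 months of treatment will return within one week of study completion". Subjects who leave early have an Early Discontinuation visit, preferably within a week of withdrawal (protocol 5.3.5).

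**Transplant (protocol 5.3.2).** "If a subject receives a liver transplant, study treatment and all treatment-related assessments will be discontinued upon transplant". Also: "The subject will continue to have subsequent planned visit assessment procedures performed".

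**Per-protocol set.** SAP 6.4.3 excludes an Albutein subject if "the subject does not receive at least 80% of the expected doses prior to the date of events (death or transplantation) or study discontinuation" or completion. No count, formula or cross-reference follows. Protocol 9.7 requires that subjects "complete at least 80% of the scheduled treatments".

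**The concern.** The 8.4 formula charges a subject for part of the next infusion before it is due. The error is largest, relative to the denominator, when few infusions have been given, so it falls on early exits. Three further gaps sit beside it: the date used in the formula, the status of transplanted subjects, and the missing count in 6.4.3.

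At stake directly is a descriptive compliance table. At stake conditionally is the PP set, which is used to repeat the primary analysis (SAP 9.1.3), the secondary analyses (SAP 9.2.7.1) and subgroup analyses (SAP 9.1.4, 9.2.8). The 80% dose rule applies to the Albutein arm only. A denominator that is too large would therefore remove early Albutein events with no matching exclusion of controls.

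**Working it through.** **1. The plan's own figure.** Day 1, Day 11, 11 monthly visits, 23 treatment-only days and Day 361 make 1 + 1 + 11 + 23 + 1 = 37 infusions. The formula at Day 361 gives 360/10 + 1 = 37. The completer count is correct.

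**2. Early exits, exact schedule.** Let t be days from randomization to exit. Infusions given = INT(t/10) + 1; expected under 8.4 = t/10 + 1.
- t = 9: 1/1.9 = 53%
- t = 19: 2/2.9 = 69%
- t = 29: 3/3.9 = 77%
- t = 39: 4/4.9 = 82%

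The ratio is below 80% for t = 3–9, 16–19 and 28–29, which is 13 days, and never after the fourth infusion. If the visit is 7 days after withdrawal, expected = (t + 7)/10 + 1 and 40 days fail: 0–19, 21–29, 34–39, 46–49 and 59.

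For scale, assume 205 subjects, exponential times, 46% events and 20% dropout per year (SAP 6.2). That gives about 31 Albutein dropouts, of whom 1.6 fall on the 13 days and 4.8 on the 40.

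**3. Transplant.** 0.8 × 37 = 29.6, so 30 infusions are needed, and the 30th is due on Day 291. A subject transplanted just after the Day 181 infusion who stays in follow-up scores 19/37 = 51% if counted as a completer under 8.4, but 19/19 = 100% if the count stops at transplant as in 6.4.3.

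**4. PP set, only if the 8.4 denominator is applied at the event date.** Under no true effect both arms have hazard h = −ln(0.54)/365 = 0.001688 per day. Dosing is exactly on schedule and the dropout of step 2 is left out.
- Events removed: 205 × 0.001688 × 13 ≈ 4.5 before allowing for survival to those days; the day-by-day sum is 4.4.
- The removed events carry about 4.4 × 13.5 = 59 person-days.
- Hazard ratio = retained events / retained person-days / h, over follow-up to 361, 181 and 91 days after randomization (SAP 9). Person-days before removal = events / h. Standard error (SE) of log HR = √(1/control events + 1/retained Albutein events).

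| Horizon | Albutein events | Retained | PP HR | SE of log HR | Shift in SE |
|---|---|---|---|---|---|
| 1 year | 93.7 | 89.3 | 0.954 | 0.148 | 0.3 |
| 6 months | 54.2 | 49.8 | 0.921 | 0.196 | 0.4 |
| 3 months | 29.5 | 25.1 | 0.854 | 0.271 | 0.6 |

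Under the plan's alternative (31% events in the Albutein arm), 2.7 events are removed and 0.602 becomes 0.577.

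**5. Other counts at the event date, no true effect.**
- Whole doses, 1 + INT(t/10): no failing day on the exact schedule, HR 1.000. With each later dose 2 days late, days 10–11, 20–21 and 30–31 fail (2.0 events, 1-year HR 0.979).
- The count proposed in the fix: no failing day, and none above 120%, for dosing at −2, 0 or +2 days from the listed days.
- Constant 12-day dosing, which is in window only if 10 ± 2 days runs from dose to dose: the 8.4 formula loses 24.8 events (1-year HR 0.759). The proposed count still fails days 23, 33–35 and 83 (1.6 events, HR 0.984).

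**The case against.** **The PP effect tests a rule that no document states.** This stands. 8.4 does not mention the PP set, and 6.4.3 has its own stop date. A reader might infer that the PP analysis is biased towards Albutein. The documents do not support that: it takes the 8.4 denominator applied at the 6.4.3 event date, a combination found in neither section. The protocol speaks of scheduled treatments, the schedule lists discrete days, and a whole-dose reading gives 1.000 on the exact schedule. What is documented is that 6.4.3 lacks a count.

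**The table may not mislabel anyone.** This stands in part. A reader might infer that the table will report fully dosed early exits as under 80% compliant. It will if infusion or overall compliance is categorised. On volume-based treatment compliance a subject given the full prepared volume scores 100%, and 8.4 does not say which measure is split. The infusion and overall compliance values themselves are wrong either way.

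**Transplanted subjects are not clearly completers.** This stands. 8.4 speaks of completing the study, SAP 5.2.6 of completing 12 months of treatment. The 37-infusion requirement is a possible reading, not a settled one.

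**The visit name is loose wording.** Probably so: the formula is written for dropouts, and protocol 8.3.8 groups End of Study and Early Discontinuation as the final visit. Reading it as the last study visit gives dropouts a date. It gives none to a subject who dies, and the fractions remain.

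**Conclusion.** The unrounded formula in 8.4 is a wrong rule, not merely a missing detail: it gives infusion compliance as low as 53% to a subject who missed nothing. Its certain effect is on infusion and overall compliance for a few early exits, about 1.6 Albutein dropouts with exit-day dating and 4.8 with a 7-day lag, under the plan's 46% and 20% rates and an assumed exponential shape.

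The effect on the PP set is conditional on 8.4 feeding 6.4.3 at the event date, and even then is about 0.3 SE at 1 year. A reader might also infer a threat to the main result. There is none: the primary analysis and the fixed sequence are ITT (SAP 6.5, 9.1.2), and PP results are sensitivity analyses. Priority: minor.

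**What to change.** In SAP 6.4.3, and in 8.4 for subjects with an early event or exit:
- Define expected doses as 1 plus the number of scheduled infusions (Day 11, 21, 31, …) whose +2-day window closed before the earliest of death, transplant or study discontinuation, plus any infusion already given in a window still open on that date.
- Use that date in 8.4 in place of the end-of-study visit, and keep 37 for event-free completers.
- State that windows are taken around the listed study days for this count only; this is a counting convention, not a dosing rule.
- Name the compliance measure that is categorised.

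The open-window clause is needed. Without it, on-schedule exits on days 10–12, 20–22, 30–32 and 40–42 would score above 120% (at day 40, 5/4 = 125%).

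The cost is about one sentence in each section and one derivation. The completer threshold stays at 30 of 37.

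Two limits should be stated. Constant 12-day dosing still fails on days 23, 33–35 and 83. The change also does not cure a one-arm 80% rule when doses are truly missed: in a simulation under no true effect, the 1-year PP hazard ratio with 5, 10, 15 and 20% of later doses missed at random was 0.985, 0.960, 0.977 and 1.118, against 0.919, 0.861, 0.828 and 0.888 with the 8.4 formula. That simulation was run once and not independently repeated.

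Separately, reconcile the interruption limit: protocol 9.7 sets it at over four consecutive weeks, SAP 6.4.3 at four or longer. The two differ only at exactly four weeks.
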